- k. All efforts should be made to perform the assessments (including blood sample collection) at the exact nominal time relative to dosing. However, assessments (including obtained blood samples) performed within 10% of the nominal time (eg, within 6 minutes of a 60 minute sample) from dosing will not be captured as a protocol deviation. The exact time of the sample collection must be noted on the source document and data collection tool (CRF).

PROTOCOL SUMMARY

Background and Rationale

PF-06835375 is a humanized, afucosyl immunoglobulin (Ig) G1 antibody against C-X-C chemokine receptor type 5 (CXCR5), a surface receptor that is expressed on B cells, bona fide follicular T helper (Tfh) cells, and circulating follicular T helper-like (cTfh) cells.^a

PF-06835375 is currently in development for the treatment of systemic lupus erythematosus (SLE). However, there is potential utility for targeting CXCR5 for the treatment of systemic autoimmune diseases more broadly. Therefore, other diseases, such as rheumatoid arthritis (RA), remain under consideration given their shared underlying pathophysiology of aberrant humoral immune responses involving B cells and Tfh cells.

CXCR5 is expressed by B cells, bona fide Tfh cells, and cTfh cells and, mediates their trafficking to and participation in germinal center (GC) immune responses.¹ GCs, a critical component of the humoral immune response, are sites where antigen-activated B cells undergo somatic hypermutation and immunoglobulin (Ig) class switching of the antibodies they produce. Bona fide Tfh cells provide instructive signals to aid this process, which culminates in the production of affinity-matured antibodies. Humoral “memory” of the GC immune response is maintained by long-lived plasma cells, which sustain antibody levels, and by memory B cells, which, upon re-challenge with antigen, trigger secondary GC immune responses with cognate help from memory Tfh cells that lead to the production of more high-affinity plasma cells.² cTfh cells are thought to differentiate into bona fide Tfh cells upon re-encountering antigen to support these memory responses, as well.³

PF-06835375 is a selective antibody directed against the CXCR5 receptor that has two distinct mechanisms of action: (1) depletion of CXCR5-positive cells through antibody-dependent cellular cytotoxicity (ADCC), and (2) antagonism of C-X-C Motif Chemokine Ligand 13 (CXCL13)-dependent signaling. By utilizing an antibody that is also antagonistic, cells that escape killing may still be inhibited from trafficking to and participating in GC immune responses. As such, the working hypothesis is that by targeting CXCR5 through a combination of depletion and antagonism, PF-06835375 will effectively impair autoreactive GC reactions, including humoral memory responses, thereby suppressing autoantibody maturation and production known to, in part, underlie autoimmune disease pathology.

The goal of this first in human (FIH) study is to evaluate the safety, tolerability, pharmacokinetics (PK), and pharmacodynamics (PD) of PF-06835375. In particular, PD characterization will include assessment of magnitude and duration of CXCR5-positive cell

^a Bona fide Tfh cells are located within lymphoid organs (ie, spleen, lymph nodes, tonsils, Peyer's patches, and mucosa-associated lymphoid tissue). cTfh cells are located in the peripheral blood.

depletion and recovery. Inhibition of the humoral immune responses via PF-06835375-mediated depletion of CXCR5-positive cells offers the potential for clinical evaluation in a population of seropositive autoimmune subjects. Consequently, a mixed population of seropositive SLE or RA subjects will be enrolled into this study.

Objectives and Endpoints

Primary Objective:	Primary Endpoints:

 To evaluate the safety and tolerability of single and multiple ascending intravenous (IV) and subcutaneous (SC) doses of PF-06835375 in subjects with SLE and RA. 	
 Incidence of dose limiting or treatment related adverse events (AEs). Incidence, severity and causal relationship of treatment emergent AEs (TEAEs) and withdrawals due to TEAE. Incidence of abnormal chemistry, hematology, and urinalysis laboratory findings through the end of study. Abnormal and clinically relevant changes in vital signs and electrocardiogram (ECG) parameters. Incidence of infections.
Secondary Objectives:	Secondary Endpoints:

 To evaluate the effect of PF-06835375 on depletion of circulating CXCR5 positive B cells and cTfh cells over time in subjects with SLE and RA. To characterize pharmacokinetics (PK) profile of PF-06835375 in subjects with SLE and RA. To evaluate immunogenicity of PF-06835375 in subjects with SLE and RA. 	
 Change from baseline in the number of circulating CXCR5 positive B cells and cTfh cells on Day 29 single dose of PF-06835375 and at Week 8 following multiple doses of PF-06835375. Serum PF-06835375 PK parameters after single and multiple doses: 
 Single Ascending Dose Phase: C_{max}, T_{max}, AUC_{inf}, AUC_{last}. Multiple Ascending Dose Phase: 
 First Dose: C_{max}, T_{max}, AUC_{tau}. Multiple Dose: C_{max}, T_{max}, AUC_{last}, AUC_{tau}, C_{min} and observed accumulation ratio (R_{ac}), peak-to-trough ratio (PTR). Incidence of development of anti-drug antibodies (ADAs)/neutralizing antibodies (Nabs).
CCI	

Study Design

This is a Phase 1, randomized, multi-center, double-blind, sponsor open, placebo-controlled, single and multiple dose-escalation study to evaluate the safety, tolerability, pharmacokinetics, and pharmacodynamics of PF-06835375 in subjects with seropositive SLE or RA. Both intravenous (IV) and subcutaneous (SC) routes of administration will be tested.

This study will include two parts: Part A, consisting of approximately eight single ascending dose (SAD) cohorts, and Part B, consisting of approximately 6 multiple ascending dose (MAD) cohorts. Cohorts in Part A will be initiated sequentially. Subjects in Part B will receive two doses of investigational product, first dose on Day 1 and second dose on Day 29, and will be enrolled concurrently with Part A following the completion of the initial cohorts in Part A (See [Section 3.3](#)). Subjects who are randomized in Part A will not be eligible to participate in Part B of this study.

This study will enroll up to a total of approximately 112 subjects at approximately 10 sites. Individual subjects are expected to stay in the study approximately 6-12 months (including screening), contingent on meeting criteria described for the end of study (See [Section 3.5](#)). Subjects who withdraw from the study may be replaced at the discretion of the sponsor. A replacement subject will receive the same treatment as the withdrawn subject.

Both SLE and RA subjects will be enrolled into this study. Minimum disease activity (ie, Systemic Lupus Erythematosus Disease Activity Index 2000, CCI [REDACTED], or Disease Activity Score 28, DAS28) cutoffs is not required for entry as inclusion criteria. All subjects

in both Part A and B will be followed for a minimum of 16 weeks prior to being able to qualify for study completion based on the cellular recovery (See [Section 3.5](#)).

It is at the sponsor's discretion to dose escalate (See [Section 3.4.1](#)), to repeat the same dose, or to test a lower dose based on emerging data.

Throughout the study, B cell counts obtained from CLIA (Clinical Laboratory Improvement Amendments) certified central lab will be used for clinical decision making (inclusion/exclusion criteria, dose escalation, initiation of Part B and for the end of study criteria).

Study Treatments

For this study, the investigational product is PF-06835375 or placebo.

PF-06835375 50 mg/mL injection is presented as a sterile solution for subcutaneous (SC) and intravenous (IV) administration.

Placebo for PF-06835375 injection is presented as a sterile solution for SC and IV administration.

In addition, Pfizer Global Clinical Supply (GCS), Worldwide Research and Development (WRD) will provide **CCI** vaccine. **CCI** will be purchased from commercial sources and will be packaged and presented with appropriate labels.

CCI

All study treatments will be administered at the investigational site as detailed in the investigational product (IP) Manual.

Statistical Methods

Detailed methodology for summary and statistical analyses of the data collected in this study is outlined in the protocol and further detailed in a statistical analysis plan (SAP), which will be maintained by the sponsor. The SAP may modify what is outlined in the protocol where appropriate; however, any major modifications of the primary endpoint definitions or their analyses will also be reflected in a protocol amendment.

The final analysis will be conducted when all subjects have completed all study visits. In addition, unblinded data will be analyzed when all subjects have completed Week 16 visit or discontinued. This analysis may take place prior to the enrollment of the optional cohort.

Adverse events, Electrocardiograms (ECGs), blood pressure, pulse rate, oral temperature, continuous cardiac monitoring, and safety laboratory data will be reviewed and summarized on an ongoing basis during the study to evaluate the safety of subjects. Any clinical laboratory, ECG, vital sign abnormalities of potential clinical concern will be described. Safety data will be presented in tabular and/or graphical format and summarized descriptively, where appropriate.

The PK concentration population is defined as enrolled subjects who received at least one dose of PF-06835375 and have at least 1 concentration. The PK parameter analysis population is defined as all enrolled subjects who received at least one dose of PF-06835375 and that have at least 1 of the PK parameters of interest. Samples from subjects who received the placebo will not be analyzed routinely.

The pharmacodynamic (PD) analysis population is defined as all randomized subjects treated who have at least one PD assessment in at least one cohort. PD assessments will include but not limited to **CCI** [REDACTED] data, soluble protein analytes, whole-blood ribonucleic acid (RNA) (inflammation and disease-related) and responses to vaccines. The data will be summarized and plotted by treatment group and sampling time.

CCI
[REDACTED]

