Administration of PF-06835375 or placebo ^{bb}			X						X												
CCI																					
Monitoring																					
Contraception check	X	X		X	→	→	→	X		X	→	→	→	→	→	→	→	→	→	→	X
Serious and non-serious adverse event monitoring	X	→	→	→	→	→	→	→	→	→	→	→	→	→	→	→	→	→	→	→	X
Concomitant treatment(s)		X	→	→	→	→	→	→	→	→	→	→	→	→	→	→	→	→	→	→	X
TB monitoring ^{dd}		X		X	→	→	→	X		X	→	→	→	→	→	→	→	→	→	→	X
Infections monitoring ^{ee}	X	X	→	→	→	→	→	→	→	→	→	→	→	→	→	→	→	→	→	→	X
Infusion/Injection Site Reactions ^{ff}			X	→	→	X			X	→	X										

Abbreviations: →= ongoing/continuous event; ACR/EULAR = American College of Rheumatology/European League Against Rheumatism; CCI [REDACTED]
BAFF = B-cell activating factor; CCI [REDACTED] C-SSRS = Columbia-Suicide Severity Rating Scale; CRU = clinical
research unit; ECG = electrocardiogram; ESR = erythrocyte sedimentation rate; FSH = follicle-stimulating hormone; HIV = human immunodeficiency virus;
CCI [REDACTED] Ig = Immunoglobulin; IGRA = Interferon gamma release assay; JCV = JC virus; PK = Pharmacokinetic; RA = rheumatoid arthritis;
SLE = systemic lupus erythematosus; CCI [REDACTED] SLICC= Systemic Lupus International Collaborating Clinics;
TB = tuberculosis.

- a. Day relative to start of study treatment (Day 1).
- b. Prior to admission to the research unit, review changes in the subject's medical history, concomitant medications and medical procedures since the Screening visit, perform contraception check and confirm that there are no changes to subject's eligibility. If a subject has any clinically significant, study related abnormalities at the conclusion of a scheduled inpatient portion of the study on Day 2 or at the end of the outpatient visit on Day 29, it is at the investigator's discretion to ask the subject to remain in the clinical unit until it is safe for outpatient follow up. The investigator must promptly notify the sponsor clinician or medical monitor. If the subject is unable or unwilling to remain in the clinical unit, the investigator should make every effort to arrange follow up evaluations at appropriate intervals. All Day 2 assessments should be completed prior to discharge from the research unit.
- c. Day 30 phone visit to occur one day after administration of IP on Day 29. It is at investigator's discretion to conduct an in clinic visit instead of a phone visit.

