- Only assessments with post-dose time points are included in this table. For these assessments, pre-dose time points are also included, as applicable. For a complete list of pre-dose assessments, please refer to the [Schedule of Activities](#) for Parts A and B above.
- Applies only to Day 1. Scheduled assessments on Day 29 will finish 8 hours post-dose.
- Full physical exam will be conducted on Day 1 pre-dose. A limited physical exam will be conducted on Day 29 pre-dose.
- A limited physical exam will be conducted 6 hours post-dose on both dosing days: Day 1 and Day 29. If any new adverse reactions are observed after injection/infusion on these dosing days and these AEs have not resolved by 6 hours post-dose or if any safety concerns, a limited physical exam will be conducted at 12-hours post-dose on Day 1 and at 8 hours post-dose on Day 29 instead.
- ECGs will be collected in triplicate in Part A on Days 1, in Part B on Days 1 and 29.

- f. Includes hematology, chemistry and urinalysis. Fasting is not required.
- g. PK samples will be collected preferably after vital signs and ECG. A pre-dose PK sample will be collected within approximately 1 hour prior to dosing. A PK sample will be collected at the end of infusion (this sample at the end of infusion pertains only to IV cohorts and does not pertain to SC cohorts). If the end of infusion is within 10 minutes of scheduled PK sample, then only the scheduled sample will be collected. If infusion duration is greater than 2 h and 10 min, then the scheduled 2 hour post-dose PK sample will not be collected.

C
C
I
C
C

- j. For SC administration, subjects will be monitored continuously for injection site reactions for 30 minutes following study drug administration and then at least at 0.5, 1, 2, 3, 4, 6, 8 hours post-dose. For IV administration, subjects will be continuously monitored for infusion site reactions from start of drug administration until the end of infusion and then at least every 30 min post-dose until end of Day 1/Day 29. Infusion/injection site reactions may be monitored beyond the time points indicated in the [Schedule of Activities](#) based on investigator's assessment.

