3. STUDY DESIGN

3.1. Study Overview

This is a Phase 1, randomized, multi-center, double-blind, sponsor open, placebo-controlled, single and multiple dose-escalation study to evaluate the safety, tolerability, pharmacokinetics, and pharmacodynamics of PF-06835375 in subjects with seropositive SLE or RA. Both IV and SC routes of administration will be tested.

This study will include two parts: Part A, consisting of approximately eight single ascending dose (SAD) cohorts, and Part B, consisting of approximately 6 multiple ascending dose (MAD) cohorts. Fewer cohorts may be included in each part at Sponsor's discretion. Cohorts in Part A will be initiated sequentially. Subjects in Part B will receive two doses of investigational product (first dose on Day 1 and second dose on Day 29), and will be enrolled concurrently with Part A following the completion of the initial cohorts in Part A (See [Section 3.3](#)). Subjects who are randomized in Part A will not be eligible to participate in Part B of this study.

[figure not shown]
This study will enroll up to a total of approximately 112 subjects at approximately 10 sites.

The study includes a Screening visit to assess eligibility and subsequent visits for a minimum of 16 weeks. Subjects who meet the end of study criteria (See [Section 3.5](#)) will have one follow-up phone call visit which will represent the end of study visit. Subjects, who do not meet the criteria to leave the study at Week 16, will continue with clinic visits every four weeks until Week 52 and then every 12 weeks until they meet these criteria. Overall, subjects are expected to stay in the study approximately 6-12 months (including screening). Subjects who withdraw from the study may be replaced at the discretion of the sponsor. A replacement subject will receive the same treatment as the withdrawn subject.

Both SLE and RA subjects will be enrolled into this study. Minimum disease activity (ie, [CCI](#) [REDACTED] or DAS28 cutoffs) is not required for entry as inclusion criteria. All subjects in both Part A and B will be followed for a minimum of 16 weeks prior to being able to qualify for study completion based on the cellular recovery (See [Section 3.5](#)).

It is at the sponsor's discretion to dose escalate (See [Section 3.4.1](#)), to repeat the same dose, or to test a lower dose based on emerging data.

[CCI](#)

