5.4.3.1.2. Subcutaneous Administration

Blinded subcutaneous (SC) PF-06835375 or placebo will be administered at the investigative site or clinic. In Part B (MAD), the planned route of administration will be SC, however safety, tolerability, PK and PD data from the Part A (SAD) will be assessed prior to initiating Part B to determine route of administration. Please refer to the IP manual for specific instructions.

The preferred body location of the SC injections is in the abdomen. If abdominal injections are not possible, arm or thigh locations may also be used. If an arm is used for the SC injection, the opposite arm should be used for the blood sample collections for PK analyses.

CCI

CCI

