$t_{1/2}^{\text{a}}$	Terminal half-life	$\text{Log}_e(2)/k_{\text{el}}$, where k_{el} was the terminal phase rate constant calculated by a linear regression of the log-linear concentration-time curve
CCI		
$AUC_{\text{last}}(\text{dn})$	Dose normalized AUC_{last}	$AUC_{\text{last}}/\text{dose}$
C_{min}	Lowest concentration observed during the dosing interval	Observed directly from data
R_{ac}	Observed accumulation ratio	
$R_{\text{ac}}, C_{\text{max}}$	Observed accumulation ratio for C_{max}	$MD AUC_{\tau}/\text{Day 1 } AUC_{\tau}$
PTF	Peak-to-trough fluctuation at steady state	$MD C_{\text{max}}/\text{Day 1 } C_{\text{max}}$ $(C_{\text{max}} - C_{\text{min}})/C_{\text{av}}$

a. If data permitted.

Abbreviations: dn = dose normalized to 1 mg, DOF = duration of the IV infusion dose, IV = intravenous, MAD = multiple ascending dose, SC = subcutaneous.

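### Part B SC cohorts: no PK sample is scheduled between 8 h after the second dose and Day 36, so the AUC accumulation ratio reads low, as does the Cmax ratio if SC Tmax is earlier than about 5 days

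*Protocol*

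**What the plan says.** Part B gives two doses, "first dose on Day 1 and second dose on Day 29" (Protocol 3.1). On route, "In Part B (MAD), the planned route of administration will be SC" (Protocol 5.4.3.1.2), and SAP Table 1 lists B1 to B5 as SC with the actual doses.

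On dosing days PK is drawn pre-dose and at 2, 4, 6, 8 and 12 h. The footnote to the 12 h column reads "Applies only to Day 1. Scheduled assessments on Day 29 will finish 8 hours post-dose". The extra end-of-infusion sample is for IV cohorts only. After the first dose, PK is also marked on Days 2, 4, 8 and 15 and pre-dose on Day 29.

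After the second dose, the Part B schedule has "Day 30 phone visit to occur one day after administration of IP on Day 29". The footnote adds "It is at investigator's discretion to conduct an in clinic visit instead of a phone visit", but no PK draw is attached to that option. The next visit is Day 36.

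The "observed accumulation ratio" is a named secondary endpoint, as are multiple-dose Cmax, Tmax and AUCtau. Protocol Table 6 defines Rac as second-dose AUCtau over Day 1 AUCtau and Rac,Cmax as second-dose Cmax over Day 1 Cmax, with AUC by the linear/log trapezoidal rule. SAP Tables 3 and 5 summarise these quantities descriptively. SAP 7.3 uses actual sampling times and leaves an individual's known biased estimate out of the summaries. It has no rule for a difference that the schedule builds into every SC subject.

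**The concern.** The two halves of each ratio come from different sampling grids. An SC antibody is absorbed over days, and the second-dose profile has nothing between 8 h and 7 days. A straight trapezoid across that gap cuts off the rise in the AUC. If the peak falls inside the gap, the highest observed second-dose value is the one at 7 days. The first-dose profile has samples at 12 h, 1 day and 3 days to catch the same part of the curve.

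At stake is the reading of accumulation. Ratios that are too low, with an observed Tmax that moves later, could be taken for faster clearance or poorer bioavailability on repeat dosing. They could also be taken for an anti-drug-antibody effect, which Protocol 9.6 says may be examined.

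**Working it through.** **Plan's own figure.** Protocol Table 1, cohort B4 (10 mg SC): Cav = 19.5/28 = 0.696 (stated 0.698); safety multiple = 261/0.698 = 374 (stated 374). No accumulation ratio and no SC Tmax or absorption rate is stated, so the bias needs a model.

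**Inputs from the documents.** CL = 10 mg / 40.8 µg·day/mL = 0.245 L/day (cohort A6). V1 = 10 mg / 4.2 µg/mL ≈ 2.4 L. SC bioavailability is 60%; it cancels in the ratios. Doses are 28 days apart.

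**Assumptions.** Linear two-compartment model, Q 0.5 L/day, V2 2.4 L, first-order absorption ka. This gives IV Cmax 4.11, second-dose IV Cmax 4.56 and Cav 1.355, against the protocol's 4.2, 4.78 and 1.36.

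**Grids.** Dose 1: 0, 2, 4, 6, 8, 12 h and 1, 3, 7, 14, 28 days. Dose 2: 0, 2, 4, 6, 8 h and 7, 14, 28 days, the last three being Days 36, 43 and 57. These three are assumed: in the copy available the Part B PK row is not legible after Day 29.

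**One case in full (ka 0.28 per day, first-dose Tmax 4.4 days, 10 mg).**
- Dose 1 AUCtau: true 17.29, on its grid 17.08.
- Dose 2 AUCtau: true 22.44, on its grid 20.59.
- Rac: true 22.44/17.29 = 1.298; as planned 20.59/17.08 = 1.206; error −7.1%.
- Cmax: true 1.241/0.974 = 1.274; as planned 1.138 (7 days) / 0.927 (3 days) = 1.228; error −3.6%.
- Common time points: dose 1 AUCtau becomes 15.43, so Rac = 20.59/15.43 = 1.334, error +2.8%. Rac,Cmax = 1.138/0.902 = 1.26, error −1.0%.

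**Across absorption rates** (true ratio, then ratio as planned):

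| ka | Tmax, dose 1 (days) | Rac | Rac,Cmax | Matched Rac error |
|---|---|---|---|---|
| 0.12 | 8.7 | 1.438 → 1.403 (−2.4%) | 1.437 → 1.455 (+1.2%) | +2.3% |
| 0.18 | 6.2 | 1.349 → 1.290 (−4.4%) | 1.345 → 1.328 (−1.3%) | +2.4% |
| 0.25 | 4.8 | 1.308 → 1.225 (−6.3%) | 1.290 → 1.273 (−1.3%) | +2.7% |
| 0.28 | 4.4 | 1.298 → 1.206 (−7.1%) | 1.274 → 1.228 (−3.6%) | +2.8% |
| 0.30 | 4.2 | 1.292 → 1.195 (−7.5%) | 1.265 → 1.186 (−6.3%) | +2.9% |
| 0.40 | 3.4 | 1.275 → 1.155 (−9.4%) | 1.234 → 1.028 (−16.7%) | +3.3% |
| 0.60 | 2.6 | 1.260 → 1.115 (−11.5%) | 1.201 → 0.858 (−28.5%) | +3.8% |

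From ka 0.28 upward, observed Tmax moves from 3 days after dose 1 to 7 days after dose 2 with no change in kinetics. At ka 0.25 and below it is 7 days for both.

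**Which rows fit Table 1's SC figures (Cmax 1.08, AUCtau 19.5)?** With 60% bioavailability, ka 0.18 gives second-dose Cmax 1.083 but AUCtau 22.2, about 14% too high. Scaling bioavailability to give AUCtau 19.5 moves the Cmax match to ka 0.28, the case worked above. Refitting the other parameters with Q fixed between 0.2 and 2.5 L/day gives Rac errors of −5.7% to −8.0% against dose 1's own grid. Rac,Cmax errors in those fits run from 0 (Tmax 6.0 days) to −20% (Tmax 1.6 days), so Table 1 pins down the Rac error far better than the Rac,Cmax error.

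**Visit window.** Day 36 is allowed ±3 days and Day 8 ±1 day. In a similar model (Q 0.7 L/day, V2 2.6 L, ka 0.25), Rac,Cmax is off by +3% if the sample is drawn on Day 33 and by −12% if drawn on Day 39.

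**The case against.** The strongest reply is that Day 36 and Day 8 are both 7 days after a dose. If SC Tmax is about 5 days or later, the two Cmax values are taken at nearly the same point and Rac,Cmax is sound; at Tmax 8.7 days it even reads slightly high. That stands. A reader might infer that the second profile always misses the peak and that both ratios must be low. The documents give no SC Tmax and do not support that.

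Two larger readings also fail. The −29% case needs ka 0.6, where second-dose Cmax is 1.56 against Table 1's 1.08. Errors of −16% to −26% in Rac appear only with an assumed clearance of 1.0 L/day, four times what Table 1 implies. One caveat runs the other way: Table 1 does not say which dose its SC Cmax refers to, and a first-dose reading would imply faster absorption and a larger Cmax error.

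A reader might also take the Part B PK row to mean that nothing is drawn after Day 29, so that second-dose AUCtau could not be calculated. The row is too damaged to confirm or rule out later draws, so no such claim is made.

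Finally, the consequence is limited. PK is descriptive (Protocol 9.1; SAP 4.2), cohorts plan 6 active subjects, and concentrations are listed with actual times. The escalation limit is a Cav of 261 µg/mL. In the worked case second-dose AUCtau itself is 8% low (20.59/22.44 = 0.918), which would take the smallest planned SC multiple only from 123 to 123 × 0.918 ≈ 113. All of this stands and lowers the severity. It does not remove the mismatch, which neither document mentions.

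**Conclusion.** The point holds in a limited form. With draws on Days 36, 43 and 57, Rac reads low in every absorption scenario examined: about −4% to −8% in models consistent with Table 1, and up to about −12% with faster assumed absorption. Rac,Cmax is low only if SC Tmax is earlier than about 5 days: roughly −4% to −6% at 4.2 to 4.4 days and −17% at 3.4 days. With a later Tmax it is essentially unbiased. A shift of observed Tmax to 7 days after the second dose may come from the schedule alone.

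The gap is read directly from the schedule. The sizes rest on linear kinetics, the assumed absorption and distribution terms, and the unconfirmed later draws. The point applies to SC dosing only. Severity is low to moderate.

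**What to change.** Change the SAP only, for Part B SC cohorts.

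1. Report Rac and Rac,Cmax from the time points sampled after both doses, alongside the Table 6 ratios. For these ratios only, drop 12 h, Day 2 and Day 4 from the first-dose profile.
2. Keep the full first-dose profile for first-dose Cmax, Tmax and AUCtau.
3. Footnote second-dose Cmax and Tmax as unresolved between 8 h and Day 36, and do not compare Tmax between doses.
4. List the actual times behind each ratio and interpret Rac,Cmax with caution.

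The cost is SAP wording and one further noncompartmental run on samples already planned; confirm first that PK is drawn on Days 36, 43 and 57. The downside is that the matched Rac is slightly high (about +2% to +4%), and the ±3-day against ±1-day windows leave some mismatch.

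Draws about 1 and 3 days after the second dose would be the fuller repair. In the Q 0.7 L/day model at ka 0.4 they move Rac from 1.18 to 1.30 (true 1.29) and Rac,Cmax from 1.07 to 1.27 (true 1.27). SAP 2.1 already reports the doses and unused cohorts in the past tense, so that is probably an option only for later studies.
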